## Results

### I-Demographic data

**Age:** Patients age ranged from 11.7 to 15.8 years. There was no significant difference in age between groups ( $p=0.19$ ), (Table 1, Fig.1)

**Cross bite:** In Butterfly hyrax, 73.3% of cases were bilateral, in comparison to 53.3% and 56.3% bilateral cases in Hybrid hyrax and MSE respectively; with no significant difference between groups ( $p=0.477$ ), (Table 2, Fig.2)

**Malocclusion:** In Butterfly hyrax and Hybrid hyrax, 73.3% of cases were class 3, in comparison to 75% class 3 cases in MSE; with no significant difference between groups ( $p=0.993$ ), (Table 3, Fig.3)

Table (1) Descriptive statistics and comparison between age between groups (ANOVA test)

	Mean	Std. Dev.	Min	Max	P value
Butterfly hyrax	14.50	1.04	11.70	15.80	0.190 ns
Hybrid hyrax	13.96	1.21	11.70	15.40	
MSE	13.81	.98	12.10	15.10	

Significance level  $p \leq 0.05$ , ns=non-significant

Table (2) Distribution of cases according to cross bite and comparison between age between groups (Chi square test)

CROSS_BITE	Groups			P value
	Butterfly hyrax	Hybrid hyrax	MSE	
Unilateral	4 (26.7%)	7 (46.7%)	7 (43.8%)	0.477 ns
Bilateral	11 (73.3%)	8 (53.3%)	9 (56.3%)	
Total	15	15	16	

Significance level  $p \leq 0.05$ , ns=non-significant

Table (3) Distribution of cases according to cross bite and comparison between age between groups (Chi square test)

MALOCCLUSION	Groups			P value
	Butterfly hyrax	Hybrid hyrax	MSE	
Class 1	4 (26.7%)	4 (26.7%)	4 (25%)	0.993 ns
Class 3	11 (73.3%)	11 (73.3%)	12 (75%)	
Total	15	15	16	

Significance level  $p \leq 0.05$ , ns=non-significant

[figure not shown]

Fig. (1) Bar chart illustrating mean age in different groups

[figure not shown]

Fig. (2) Bar chart illustrating distribution of unilateral and bilateral cases in different groups

[figure not shown]

Fig. (3) Bar chart illustrating distribution of malocclusion classes in different groups

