So the aim of this study was to evaluate the effect of three types of rapid maxillary expanders (conventional, Hybrid and MSE) using cone beam computed tomography (CBCT)

Aim of study

The aim of this study was to compare the effect of three types of rapid maxillary expanders (conventional, Hybrid and MSE) using cone beam computed tomography (CBCT)

The secondary outcomes

- a- Evaluation of periodontal condition of maxillary first permanent molars, both clinically and radiographically using CBCT
- b- Evaluation of Airway.

Material and Methods

Study design:

Prospective randomized controlled trial

Study setting and population:

This study will be conducted on patients seeking orthodontic treatment in the outpatient clinic, Orthodontic department, Faculty of Dental Medicine, Al-Azhar University, Cairo, Boys branch.

Eligibility criteria of population:

The patients will be selected according to the following inclusions criteria:

- 1- Patients suffering maxillary collapse with a skeletal background
- 2- Patients with unilateral or bilateral posterior crossbite.
- 3- Patients with reduced or average anterior face height.
- 4- Patients with no periodontal disease.
- 5- Patients with good oral hygiene and general health.
- 6- No systemic diseases that may affect bone quality or interfere with orthodontic treatment.
- 7- Patients with erupted maxillary permanent first molars and premolars.
- 8- Patients with no previous orthodontic treatment.

Sample size:

Sample size calculation using G power software was based on the observed effect sizes derived from previous article. ⁽²⁰⁾

The calculation indicated that for a study with a power of 0.95 and an alpha of 0.05, a total of at least 45 patients (15 patients in each group) .

Group allocation:

The patients will be classified and randomly allocated into three equal groups, using online generated randomization plan (Graph Pad) found at the website

<http://www.graphpad.com/quickcalcs/index.cfm>:

- Group (1): The conventional hyrax.
- Group (2): The Hybrid hyrax.
- Group (3): The MSE expander.

Interventions:

The current study was conducted on a total sample of forty five young adult orthodontic patients presented with transverse maxillary deficiency with an age ranged from 11-16 years.

- All patients in this study will undergo a special protocol for oral hygiene measures for one month to standardize as possible the oral hygiene measure before expansion.

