- The following diagnostic records will be taken for each patient before and after the completion of expansion treatment:
- Orthodontic study casts.
- Standardized extra-oral and intra-oral photographs.
- Panoramic and Upper occlusal radiographs.
- Other radiographic evaluations that serve the purpose of the study according to the situation.

- Radiographic analysis will be performed for each patient to evaluate the effect of the rapid maxillary expansion on the nasal airway.

Ethical consideration:

The objectives of the study will be discussed to the patients and parents and informed consent will be signed before treatment (form is attached).

Data management and analysis:

- The collected data will be statistically analyzed using SPSS.

The Institutional Ethical Committee: approval number **775/220**

References

4. Haas AJ. Rapid expansion of the maxillary dental arch and nasal cavity by opening the midpalatal suture. *Angle Orthod.* 1961;31(2):73-90.

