# **Evaluation of the Effect of Three Types of Rapid Maxillary Expanders (Conventional, Hybrid and MSE)**

**NCT05446714**

**Date of the document:14/5/2024**

### **Statistical analysis**

Data management and statistical analysis were performed using the Statistical Package for Social Sciences (SPSS) version 20. Data were explored for normality by checking the data distribution and using Kolmogorov-Smirnov and Shapiro-Wilk tests. Comparisons of normally distributed numeric variables between groups was performed by ANOVA test followed by Bonferroni post hoc test whenever a significance difference was detected. Pre and post values was compared by paired t test.

The mean difference was calculated by the formula:(Value after-value before)

Difference data were non-parametric and were compared between groups using Kruskal Wallis test.

All p-values are two-sided. P-values  $\leq 0.05$  were considered significant.

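### The arms are compared without baseline value, age or crossbite type as covariates, and comparability rests only on baseline significance tests that cannot show balance at 15 to 16 per arm

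*SAP*

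**What the plan says.** The Protocol (Group allocation) states that patients are "randomly allocated into three equal groups" and names no stratification factor.

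The SAP (Statistical analysis) compares arms by ANOVA with Bonferroni post hoc tests, compares change scores by Kruskal-Wallis because it regards them as non-parametric, and uses paired t tests within arms. No covariate appears in any between-arm comparison.

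The SAP (I-Demographic data) tests age, crossbite type and malocclusion across arms and reports each as non-significant. For age it says "There was no significant difference in age between groups" (p = 0.19). For crossbite it says "In Butterfly hyrax, 73.3% of cases were bilateral, in comparison to 53.3% and 56.3% bilateral cases in Hybrid hyrax and MSE respectively" (p = 0.477). Pre-treatment values of the outcomes are tested in the same way in the outcome tables. No standardised differences are given, and no confidence intervals for arm differences.

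**The concern.** A non-significant baseline test with 15 or 16 patients per arm does not show that the arms are alike. If a characteristic differs by chance and also predicts outcome, the unadjusted contrast in this particular sample is shifted, and the reader cannot tell by how much.

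Two features make the point worth raising. First, the Protocol itself cites a study titled "Age-dependent effects of transverse maxillary deficiency treated by microimplant-assisted rapid palatal expansion", so age is a plausible prognostic factor. A title gives neither direction nor slope. Second, the outcome tables show that baseline value is related to change for some outcomes, and the arms do not start level on one of them. An analysis that uses neither variable leaves a cheap check undone and may give up precision.

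**Working it through.** **Inputs.** Arm sizes 15/15/16 (SAP, demographic Tables 2 and 3). Age mean (SD): Butterfly 14.50 (1.04), Hybrid 13.96 (1.21), MSE 13.81 (0.98) (demographic Table 1). Outcome means and SDs are from the outcome tables. The text swaps the Butterfly and Hybrid changes for hard palate width 6; the table values are used because they match post minus pre (63.59 - 60.43 = 3.16; 62.04 - 58.67 = 3.37).

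**1. Reproduce the SAP's figures.** Age: within-arm SS = 14(1.04²) + 14(1.21²) + 15(0.98²) = 50.05. Between-arm SS = 4.03 on 2 df. F = (4.03/2)/(50.05/43) = 1.73, p = 0.189, which agrees with 0.190. Crossbite: chi-square 1.479 on 2 df, p = 0.477, which agrees.

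**2. Size of the imbalances.**
- Age, Butterfly minus MSE: 14.50 - 13.81 = 0.69 years (95% CI -0.05 to 1.43). Two-arm pooled SD 1.009, so SMD = 0.68; on the three-arm SD of 1.079 it is 0.64.
- Other age SMDs: Butterfly-Hybrid 0.48, Hybrid-MSE 0.14.
- Bilateral crossbite, 11/15, 8/15 and 9/16: SMD 0.42 for Butterfly-Hybrid and 0.36 for Butterfly-MSE.
- Hard palate width 6 before treatment: 60.43 - 58.39 = 2.04. Pooled SD = sqrt[(14 x 2.49² + 15 x 2.44²)/29] = 2.46, so SMD = 0.83. The three-arm test of this baseline gave p = 0.083.

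**3. What the age p-value can show.** Observed f = sqrt(1.73 x 2/46) = 0.27. The three-arm test has about 34% power at that f. This largely restates the data, but with the CI it shows that a gap above one year is not excluded.

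**4. Possible shift from age.** Conditional shift in the MSE-Butterfly contrast = r x SMD, where r is the within-arm correlation of age with outcome. The documents give no r; a range is assumed. With the three-arm SMD of 0.64: r = 0.2 gives 0.13 SD, r = 0.3 gives 0.19 SD, r = 0.5 gives 0.32 SD. The unadjusted MSE-Butterfly differences in change run from 1.2 to 6.6 SD in 11 outcomes checked. At r = 0.5, using 0.68, the shift is 5% of the largest and 28% of the smallest (premolar distance, 1.23 SD; left molar inclination, 1.27 SD, is next at 27%).

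**5. Precision from the age term.** Variance ratio, adjusted to unadjusted = (1 - r²) x [1 + (0.69²/50.05)/(1/15 + 1/16)] = (1 - r²) x 1.074. The ranges below run from this ratio to the ratio with the further 43/42 penalty for the lost df.
- r² = 5%: SE ratio 1.01 to 1.02, so the interval widens.
- r² = 20%: SE ratio 0.93 to 0.94.
- Break-even: r = sqrt(1 - 1/1.074) = 0.26, or 0.30 with the lost df.

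**6. The baseline value.** Within-arm correlation of baseline with change = (SDpost² - SDpre² - SDchange²)/(2 x SDpre x SDchange).
- Width 6: Butterfly (2.15² - 2.49² - 1.54²)/(2 x 2.49 x 1.54) = -0.51; Hybrid -0.47; MSE -0.79; pooled -0.55.
- Width 4: -0.41, -0.63, -0.41.

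For width 6 the pooled within-arm slope is the sum of (n - 1) x covariance over the sum of (n - 1) x SDpre² = -73.1/301.3 = -0.243 mm per mm. A 2.04 mm head start corresponds to 0.243 x 2.04 = 0.50 mm less expected change in Butterfly. The MSE-Butterfly difference would move from 5.91 - 3.17 = 2.74 mm to about 2.24 mm. The variance ratio is (1 - 0.55²) x [1 + (2.04²/301.3)/(1/15 + 1/16)] = 0.698 x 1.107 = 0.77, an SE ratio of about 0.88 (0.89 with the lost df).

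**7. Rows not usable for step 6.** The SD of a change cannot be smaller than the gap between the pre and post SDs. Butterfly nasal floor molar fails (5.07 - 1.67 = 3.40, against 1.49), and so does Butterfly premolar distance (4.60 - 2.55 = 2.05, against 1.83). These rows need checking at source, and the 1.23 SD for premolar distance inherits that doubt.

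**The case against.** A reader might infer that the MSE advantage is an artefact of age, because MSE is the youngest arm and shows the most skeletal expansion. The documents do not support this:
- Hybrid is only 0.15 years older than MSE, yet shows less change: nasal floor molar 2.60 against 4.38, width 6 3.37 against 5.91, width 4 5.09 against 6.35, anterior suture 3.67 against 5.69, posterior suture 3.06 against 5.16.
- Butterfly and Hybrid differ by 0.54 years, yet are close on nasal floor molar (2.20, 2.60), width 6 (3.17, 3.37) and anterior suture (3.47, 3.67).
- Explaining MSE-Butterfly skeletal differences of 1.84 to 3.02 mm by age alone would need slopes of 1.84/0.69 = 2.7 to 3.02/0.69 = 4.4 mm per year.

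It is also fair to say that randomisation makes these chance imbalances, so the unadjusted estimator is not biased over repeated randomisation. By simulation, a gap of 0.68 SD or more in at least one of three pairs arises in about 16% of trials of this size. The SAP never says the arms are balanced, nor that these tests are why it did not adjust. Nothing in the documents links crossbite type to any outcome. Choosing covariates after seeing imbalance is data-driven.

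All of this stands, and it limits the claim. It does not rescue non-significance as evidence of comparability. Nor does it answer the baseline-value term, whose relevance for hard palate width can be read from the SAP's own SDs.

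**Conclusion.** The point holds as a criticism of method. Comparability is assessed only by tests too weak to establish it, and the analysis leaves out three variables already in hand. The age gap between Butterfly and MSE is 0.68 SD. Its effect on the contrast is a conditional shift of about r x 0.64 to 0.68 SD, with size and sign unknown because the documents give no age-outcome correlation. For width 6, the baseline imbalance alone would move the MSE-Butterfly difference by about 0.5 mm out of 2.74. That assumes the reported SDs are right and a common linear within-arm slope; part of the correlation may be measurement error.

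The large skeletal differences are unlikely to be overturned. The smaller contrasts, premolar distance and left molar inclination, are the most exposed.

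Two stronger readings should not be drawn. One is that the unadjusted results are biased in favour of MSE: the documents give no direction for the age effect, and the Hybrid comparison argues against age as the explanation. The other is that adjustment necessarily tightens the intervals: for age, that is true only if r exceeds about 0.26 to 0.30.

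**What to change.** 1. Replace the baseline p-values with standardised differences for each pair of arms.
2. For each outcome, add an ANCOVA of the post value on arm and baseline value, with age (continuous) and crossbite type (unilateral or bilateral) added. Modelling change instead gives the same arm differences once baseline is in the model. Posterior suture opening is zero for everyone before treatment, so its baseline term drops out.
3. Report adjusted arm differences with 95% CIs, and check residuals, because the SAP describes the differences as non-parametric.
4. Label the adjusted model post hoc, since the document already contains results, and show it beside the unadjusted analysis.
5. Check the impossible SD rows before fitting.

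Cost: no new data, a re-run and some SAP wording. The model uses three of the 43 error degrees of freedom (46 - 3), leaving 40. The baseline term should improve precision for outcomes such as hard palate width. The age term may slightly widen the MSE-Butterfly interval if age is weakly related to outcome.

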## II- Outcomes

### I- Comparison between Hybrid and conventional hyrax groups

- **Molar distance:** There was no significant difference between groups in pre values ( $p= 0.094$ ). Regarding post treatment, The mean value recorded in Hybrid hyrax ( $52.21\pm2.59$ ) was significantly higher than that recorded in Butterfly hyrax ( $49.43\pm2.41$ ) ( $p= .016$ ). Moreover, there was a statistically significant difference between groups regarding the amount of change (difference) by treatment ( $p=0.000$ ), with the highest value recorded in MSE ( $8.88\pm1.58$ ), followed by Hybrid hyrax ( $7.24\pm1.77$ ) and the lowest value recorded in Butterfly hyrax ( $5.88 \pm 1.39$ ), (Table1, Fig.1, 11).
- **Premolar distance:** There was no significant difference between groups in pre values ( $p= 0.058$ ). Regarding post treatment, The mean value recorded in Butterfly hyrax ( $43.67\pm2.55$ ) and Hybrid hyrax ( $42.73\pm2.7$ ) was significantly higher than that recorded in MSE ( $38.46 \pm2.61$ ), ( $p= .000$ ). Moreover, the mean value of amount of change (difference) recorded in Butterfly hyrax ( $6.68\pm1.83$ ) and Hybrid hyrax ( $6.08\pm1.84$ ) was significantly higher than that recorded in MSE ( $4.43 \pm1.82$ ), ( $p= .005$ ). (Table1, Fig.1, 11).
- **Molar rotation:** There was no significant difference between groups, regarding pre and post values ( $p= 0.175$ ;  $p=0.207$  respectively in right side and  $p=0.06$ ;  $p=0.07$  in left side). There was no significant difference between groups regarding the amount of change (difference) by treatment ( $p=0.503$  in right side and  $p=0.757$  in left side), (Table 1, Fig 2,12)
- **Premolar rotation:** there was no significant difference between groups, regarding pre and post values for the right side ( $p= .566$ ;  $p=.609$  respectively) and the left side ( $p=.455$ ;  $p=.283$  respectively). Moreover, there was no statistically significant difference between groups regarding the amount of change (difference) by treatment in the right side and left sides ( $p=0.084$ ;  $p= .410$  respectively), (Table 1, Fig.3,12)
- **Nasal floor molar:** There was no significant difference between groups in pre values ( $p= 0.058$ ) and post value ( $p=0.397$ ). There was a statistically significant difference between groups regarding the amount of change (difference) by treatment ( $p=0.000$ ), with the highest value recorded in MSE ( $4.38\pm0.85$ ), followed by Hybrid hyrax ( $2.6\pm1.04$ ) and the lowest value recorded in Butterfly hyrax ( $2.2\pm 1.49$ ), (Table 2, Fig.4, 13).
- **Nasal floor premolar:** There was no significant difference between groups in pre values ( $p= 0.701$ ). Regarding post treatment value, there was a statistically significant difference between groups ( $p=0.001$ ), with the highest value recorded in MSE ( $39.73\pm2.27$ ), followed by Hybrid hyrax ( $38.63\pm1.77$ ) and the lowest value

recorded in Butterfly hyrax ( $37.04 \pm 1.17$ ). Moreover, regarding the amount of change (difference) by there was a statistically significant difference between groups ( $p=0.000$ ), with the highest value recorded in MSE ( $4.87 \pm 0.62$ ), followed by Hybrid hyrax ( $3.43 \pm 0.74$ ) and the lowest value recorded in Butterfly hyrax ( $2.47 \pm 1.02$ ), (Table 2, Fig.4, 13).

- **Hard palate maxillary width 6:** There was no significant difference between groups in pre values ( $p= 0.083$ ). Regarding post treatment, the mean value recorded in MSE ( $64.31 \pm 1.8$ ) was not significantly different from butterfly Hyrax ( $63.59 \pm 2.15$ ), but was significantly higher than that recorded in Hybrid hyrax ( $62.04 \pm 2.68$ ), ( $p= .023$ ). The mean value of amount of change (difference) recorded in MSE ( $5.91 \pm 0.92$ ) was significantly higher than that recorded in Butterfly hydrax ( $3.37 \pm 0.96$ ) and Hybrid hyrax ( $3.17 \pm 1.54$ ), ( $p= .000$ ). (Table 2, Fig. 5, 14).
- **Hard palate maxillary width 4:** There was no significant difference between groups in pre values ( $p= 0.677$ ). Regarding post treatment, the mean value recorded in MSE ( $40.34 \pm 1.56$ ) was significantly higher than that recorded in butterfly hyrax ( $38.17 \pm 1.76$ ), ( $p= .002$ ). The mean value of amount of change (difference) recorded in MSE ( $6.35 \pm 1.25$ ) was significantly higher than that recorded in Butterfly hydrax ( $4.51 \pm 1.28$ ) and Hybrid hyrax ( $5.09 \pm 1.16$ ), ( $p= .001$ ). (Table 2, Fig. 5, 14).
- **Molar inclination:** There was no significant difference between groups, regarding pre and post values ( $p= 0.353$ ;  $p=0.734$  respectively in right side and  $p=0.312$ ;  $p=0.892$  in left side). The mean value of amount of change (difference) recorded in MSE was significantly higher than that recorded in Butterfly hydrax and Hybrid hyrax, ( $p= .000$  in right side and  $p=0.003$  in left side). (Table 2, Fig 6, 15)
- **Premolar inclination:** There was no significant difference between groups, regarding pre values ( $p= 0.191$  in right side and  $p=0.355$  in left side). Post treatment, the mean value recorded in Butterfly hyrax was significantly higher than the other groups ( $p=0.003$  in right side and  $p=0.000$  in left side). The mean value of amount of change (difference) recorded in MSE was significantly higher than that recorded in Butterfly hydrax and Hybrid hyrax, ( $p= .000$  in right side and  $p=0.000$  in left side). (Table 2, Fig 7, 15)
- **Arch depth:** There was no significant difference between groups, regarding pre values ( $p= 0.064$ ). Post treatment, the mean value recorded in MSE was significantly lower than the other groups ( $p=0.007$ ). The mean value of amount of change (decrease) recorded in MSE was significantly greater than that recorded in Butterfly hydrax and Hybrid hyrax, ( $p= .000$ ), (Table 3, Fig 8, 16)

- **Incisor inclination:** There was no significant difference between groups, regarding pre and post values ( $p= 0.243$  and  $p=0.922$  respectively). The mean value of amount of change (decrease) recorded in MSE was significantly greater than that recorded in Butterfly hydrax and Hybrid hyrax, ( $p= .001$ ), (Table 3, Fig 9, 18)
- **Anterior suture opening:** There was no significant difference between groups, regarding pre values ( $p= 0.290$ ). The mean value recorded in MSE post treatment was significantly higher than that recorded in Butterfly hydrax and Hybrid hyrax, ( $p= .000$ ). The mean value of amount of change (increase) recorded in MSE was significantly higher than that recorded in Butterfly hydrax and Hybrid hyrax, ( $p= .001$ ), (Table 3, Fig 10, 18)
- **Posterior suture opening:** All groups recorded a value ( $0\pm0.00$ ) pre-treatment. Post treatment, The mean value recorded in MSE was significantly higher than that recorded in Butterfly hydrax, while Hybrid hyrax recorded a significantly lower value than the other 2 groups ( $p= .000$ ). The mean value of amount of change (increase) recorded in MSE was significantly higher than that recorded in Butterfly hydrax; while Hybrid hyrax recorded a significantly lower value than the other 2 groups ( $p= .000$ ), (Table 3, Fig 10, 18)

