## II-Comparison between pre and post values Hybrid and conventional hydrax groups

Comparing the pre and post values revealed that the post treatment value was significantly higher in post value compared to the pre value in molar and premolar distance (Fig.1), right and left molar rotation (Fig.2), right and left premolar rotation (Fig.3), nasal floor first premolar and molar (Fig.4), hard palate maxillary width first molar and premolar (Fig.5), right and left molar inclination (Fig.6), right and left premolar inclination (Fig.7) and anterior and posterior suture opening (Fig.10). On the other hand, Arch depth and incisor inclination recorded significantly lower post value compared to the pre value (Fig. 8,9), (Table 1-3)

Table (1) Descriptive statistics and comparison between (ANOVA test) and within group (i.e. between pre and post value) (paired t test) regarding molar and premolar distance; molar and premolar rotation right and left

GROUP	Pre		Post		Amount of change (post-pre)			P Within group	
	Mean	Std. Dev	Mean	Std. Dev	Mean	Std. Dev	Median		
Molar distance	Butterfly hyrax	43.55	1.97	49.43 b	2.41	5.88 c	1.39	5.77	.000*
	Hybrid hyrax	44.79	4.27	52.21 a	2.59	7.42 b	1.77	7.50	.000*
	MSE	42.14	3.25	51.01 ab	2.56	8.88 a	1.58	8.95	.000*
	P value bet. groups	.094ns		.016*		.000*			
Premolar distance	Butterfly hyrax	36.99	4.60	43.67 a	2.55	6.68 a	1.83	6.20	.004*
	Hybrid hyrax	36.65	3.15	42.73 a	2.70	6.08 a	1.84	5.90	.002*
	MSE	34.03	3.12	38.46 b	2.61	4.43 b	1.82	4.85	.002*
	P value bet. groups	.058 ns		.000*		.005*			
Molar rotation right	Butterfly hyrax	58.32	4.68	59.57	4.74	1.25	.67	1.10	.000*
	Hybrid hyrax	61.50	4.54	62.54	4.42	1.04	.58	1.10	.000*
	MSE	61.95	7.38	62.99	7.26	1.04	.65	0.90	.000*
	P value bet. groups	.175ns		.207 ns		.503 ns			
Molar rotation left	Butterfly hyrax	59.75	5.31	61.17	5.27	1.42	.51	1.50	.000*
	Hybrid hyrax	64.31	5.57	65.55	5.46	1.25	.82	1.10	.000*
	MSE	60.43	5.65	61.90	5.54	1.48	1.06	1.20	.000*
	P value bet. groups	.060 ns		.070 ns		.757 ns			
Premolar rotation right	Butterfly hyrax	74.71	6.68	75.84	6.64	1.13	.40	1.10	.000*
	Hybrid hyrax	73.79	6.58	74.71	6.48	.93	.48	0.90	.000*
	MSE	76.43	7.60	77.21	7.60	.78	.42	0.75	.000*
	P value bet. groups	.566 ns		.609 ns		.084ns			
Premolar rotation left	Butterfly hyrax	74.23	6.40	75.27	6.33	1.05	.32	1.10	.000*

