	Hybrid hyrax	76.99	6.07	78.65	5.55	1.65	2.50	1.10	.000*
	MSE	75.14	5.83	76.16	5.95	1.02	.47	1.10	.000*
	P value bet. groups	.455ns		.283ns		.410ns			

Significance level p≤0.05, \*significant, ns=non-significant

Post hoc test: Within the same comparison, means sharing the same superscript letter are not significantly different

Table (2) Descriptive statistics and comparison between (ANOVA test) and within group (i.e. between pre and post value) (paired t test) regarding nasal floor, hard palate maxillary width molar and premolar; molar and premolar inclination right and left

GROUP	Pre		Post		Amount of change (post-pre)			P Within group	
	Mean	Std. Dev	Mean	Std. Dev	Mean	Std. Dev	Median		
Nasal floor 1 st .molar	Butterfly hyrax	65.13	5.07	67.33	1.67	2.20 b	1.49	1.80	.003*
	Hybrid hyrax	63.48	3.13	66.08	2.80	2.60 b	1.04	2.40	.000*
	MSE	62.00	3.36	66.38	3.07	4.38 a	.85	4.45	.000*
	P value bet. groups	.058ns		.397ns		.000*			
Nasal floor 1 st .premolar	Butterfly hyrax	34.57	1.55	37.04 c	1.17	2.47 c	1.02	2.40	.001*
	Hybrid hyrax	35.21	2.09	38.63 b	1.77	3.43 b	.74	3.50	.000*
	MSE	34.86	2.40	39.73 a	2.27	4.87 a	.62	5.00	.000*
		.701ns		.001*		.000*			
Hard palate Maxillary width 6	Butterfly hyrax	60.43	2.49	63.59 ab	2.15	3.17 b	1.54	3.10	.000*
	Hybrid hyrax	58.67	2.99	62.04 b	2.68	3.37 b	.96	3.40	.000*
	MSE	58.39	2.44	64.31 a	1.80	5.91 a	.92	6.10	.000*
	P value bet. groups	.083ns		.023*		.000*			
Hard palate Maxillary width 4	Butterfly hyrax	33.66	1.85	38.17 b	1.76	4.51 b	1.28	4.50	.001*
	Hybrid hyrax	34.22	1.79	39.31 ab	1.39	5.09 b	1.16	4.90	.001*
	MSE	33.99	1.58	40.34 a	1.56	6.35 a	1.25	6.10	.003*
	P value bet. groups	.677ns		.002*		.001*			
Right.1 st molar inclination	Butterfly hyrax	18.58	4.41	24.24	5.32	5.66 a	1.52	5.80	.000*
	Hybrid hyrax	18.43	5.33	23.27	5.20	4.85 a	2.10	6.00	.000*
	MSE	20.74	5.06	22.82	4.77	2.08 b	1.30	1.70	.000*
	P value bet. groups	.353ns		.734ns		.000*			
Left.1 st molar inclination	Butterfly hyrax	18.45	4.34	23.67	6.07	5.21 a	2.74	6.30	.000*
	Hybrid hyrax	19.09	3.08	23.71	3.68	4.62 a	1.62	4.90	.000*
	MSE	20.49	3.78	23.01	3.53	2.52 b	1.31	2.35	.000*
	P value bet. groups	.312ns		.892ns		.003*			

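### Outcome Tables 1–3 of the SAP print SDs and within-group p-values that cannot be correct; two nasal floor molar statements cannot be verified

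*SAP*

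**What the plan says.** The SAP's Statistical analysis section gives the tests: ANOVA between groups for normally distributed variables, a paired t test for pre against post, two-sided p-values and significance at .05 or below. For change it says "Difference data were non-parametric and were compared between groups using Kruskal Wallis test". The title of outcome Table 1 again names the paired t test: "and within group (i.e. between pre and post value) (paired t test) regarding molar and premolar distance".

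For nasal floor width at the first molar, the Outcomes text states "There was no significant difference between groups in pre values ( $p= 0.058$ ) and post value ( $p=0.397", and for the change, "the lowest value recorded in Butterfly hyrax ( $2.2\pm 1.49". In outcome Table 2 (row "Nasal floor 1 st .molar") the Butterfly arm shows pre 65.13 (SD 5.07), post 67.33 (SD 1.67), change 2.20 (SD 1.49) and within-group p .003. The pre-post section lists this measure among those significantly higher after treatment: "nasal floor first premolar and molar (Fig.4), hard palate maxillary width first molar and premolar (Fig.5".

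For premolar distance the text gives changes of "Butterfly hyrax ( $6.68\pm1.83$ ) and Hybrid hyrax ( $6.08\pm1.84". Outcome Table 1 shows Butterfly SDs of 4.60 before and 2.55 after, with within-group p .004.

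**The concern.** The SDs of paired measurements constrain one another. Some change SDs printed here are smaller than the pre and post SDs beside them allow, so at least one figure in each such row is wrong. Many within-group p-values also fail to match the mean and SD of change in their own row. Small change SDs make the effects look more precise than they may be, and they would carry over into any reuse of the tables. At stake for nasal floor molar are the claimed pre-post increase in Butterfly and the claimed absence of a baseline difference.

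**Working it through.** **Inputs.** Means, SDs and p-values come from outcome Tables 1–3. Those tables print no n, so group sizes of 15 (Butterfly), 15 (Hybrid) and 16 (MSE) are taken from the demographic tables.

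**Control.** One-way ANOVA from means, SDs and n gives age p = .189 (printed .190), nasal floor molar post p = .395 (.397) and premolar distance pre p = .0584 (.058). Of 35 pre/post between-group p-values, 34 reproduce within rounding.

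**The exception.** For nasal floor molar pre values, means 65.13, 63.48, 62.00 and SDs 5.07, 3.13, 3.36 give a between-group mean square of 37.93 and a within-group mean square of 15.50. F = 37.93/15.50 = 2.45 on 2 and 43 df, p = .098. Rounding of the inputs allows .097 to .100, but .058 is printed.

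**SD bound.** |SDpre − SDpost| ≤ SDchange ≤ SDpre + SDpost, whatever the sample size or distribution.
- Nasal floor molar, Butterfly: 5.07 − 1.67 = 3.40 (3.39 at the rounding limits); printed 1.49. Implied correlation (5.07² + 1.67² − 1.49²)/(2 × 5.07 × 1.67) = 1.55.
- Premolar distance, Butterfly: 4.60 − 2.55 = 2.05 (2.04 at the limits); printed 1.83. Implied correlation 1.04.
- Arch depth, Butterfly: .40 (.390 at the limits); printed .38 (at most .385). Marginal.

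**Repeated values.** In left premolar inclination the change mean and change SD are identical in each arm: 5.09, 2.06 and .80.

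**Paired t test.** t = mean change/(SDchange/√n) on n − 1 df. The largest p at any correlation uses SDpre + SDpost in place of SDchange. Three of the 54 change means are lost in the extracted text and were taken as post minus pre; none is among these 14:

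| Row | Change (SD) | p from these | Largest p at any correlation | Printed |
|---|---|---|---|---|
| Premolar distance, Butterfly | 6.68 (1.83) | 1e-9 | .0028 | .004 † |
| Premolar distance, Hybrid | 6.08 (1.84) | 4e-9 | .0013 | .002 † |
| Premolar distance, MSE | 4.43 (1.82) | 7e-8 | .0074 | .002 |
| Nasal floor molar, Butterfly | 2.20 (1.49) | .00005 | .23 (smallest .025) | .003 † |
| Nasal floor premolar, Butterfly | 2.47 (1.02) | 2e-7 | .0034 | .001 |
| Hard palate width 4, Butterfly | 4.51 (1.28) | 2e-9 | .0003 | .001 † |
| Hard palate width 4, Hybrid | 5.09 (1.16) | 1e-10 | .00002 | .001 † |
| Hard palate width 4, MSE | 6.35 (1.25) | 3e-12 | 8e-7 | .003 † |
| Anterior suture, Butterfly | 3.47 (.34) | 9e-16 | 4e-11 | .004 † |
| Anterior suture, MSE | 5.69 (.33) | 3e-20 | 7e-14 | .002 † |
| Left premolar rotation, Hybrid | 1.65 (2.50) | .023 | .59 | .000 |
| Left premolar inclination, Butterfly | 5.09 (5.09) | .0017 | .0047 | .003 |
| Left premolar inclination, Hybrid | 2.06 (2.06) | .0017 | .022 | .000 |
| Left premolar inclination, MSE | .80 (.80) | .0012 | .46 | .000 |

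The eight rows marked † cannot come from a paired t test at any correlation, given the printed means and pre/post SDs. Eleven of the 14 are printed too large and three too small.

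**Could it be an unlabelled signed-rank test?** Its asymptotic p cannot fall below .00065 at n = 15 or .00044 at n = 16. It could therefore explain the .001 values, and a rank sum of 8 gives .0031, close to the .003 for nasal floor molar Butterfly. It cannot explain three other rows. No value lies further than SD(n − 1)/√n from its mean, so every difference is positive in anterior suture Butterfly (3.47 − .34 × 14/√15 = 2.24), anterior suture MSE (4.45) and hard palate width 4 MSE (1.66). The test would then give .0007, .0004 and .0004, against .004, .002 and .003 printed.

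**What follows for nasal floor molar, Butterfly (means taken as correct).**
- Only the change SD wrong: it lies in 3.40 to 6.74, so paired p is .025 to .23, crossing .05 at SD 3.97 (correlation .75).
- Only the pre SD wrong: it is at most 1.67 + 1.49 = 3.16, so baseline p is .009 to .034.
- Only the post SD wrong: it lies in 3.58 to 6.56, so post p is .53 to .73. Both significance statements stand, but .058 and .003 still do not reproduce.
- More than one wrong: a pre SD of 3.79 to 5.07 keeps baseline p above .05. With post SD 1.67, paired p is then .05 or below if the correlation is at least .11 (pre SD 3.79) to .75 (pre SD 5.07). Pre SD 4.05 with change SD 2.38 returns both printed p-values, but only at a correlation of about 1.

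**The case against.** The strongest reply concerns consequence. Neither nasal floor statement is shown to be false. All 14 p-values stay below .05 at the printed SDs, and most are printed too large, which understates the evidence. The trial's aim is to compare three appliances, which within-group and baseline tests do not do. All of this is true and limits the claim. It does not make the printed figures right, and for nasal floor molar the correction could change what is concluded.

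Some narrower points also stand:
- A wrong post SD is the least likely nasal floor explanation, because 1.67 reproduces the printed post p. For premolar distance, 4.60 reproduces the printed baseline p, which points to the change SD there. Neither settles which entry is wrong.
- The signed-rank limits above are asymptotic. An exact test with all differences positive gives 2/2^15 = .00006 at n = 15, so it could lie behind rows printed .000, including left premolar rotation Hybrid. It does not rescue anterior suture or hard palate width 4 MSE.
- The left premolar inclination SDs appear only in the table, so a text-extraction fault cannot be wholly excluded, though three identical pairs make it unlikely. Its three mismatches may share one cause and should not be counted as independent. None of the eight unreachable p-values is in that row.

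Extraction damage does not explain the two impossible rows: the Outcomes text repeats both change SDs. In both rows the change mean equals post minus pre, so differing patient sets are unlikely.

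**Conclusion.** The concern holds. Two Butterfly rows contain SDs that cannot coexist, and a third row shows what is evidently a copied SD column. Of 54 within-group p-values, 14 disagree with the named test, 9 of them outside those rows, and 8 are unreachable by that test. The nasal floor molar baseline p recomputes to .098, not .058. The Butterfly pre-post significance and the absence of a baseline difference for that measure cannot be verified, and which of them is at risk depends on which entry is wrong. If the post SD or several entries are wrong, both could stand. The premolar distance change in Butterfly remains significant at any admissible SD (p at most .0028).

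The p-value checks assume group sizes of 15, 15 and 16 for every outcome; the SD bound does not depend on n. Between-group comparisons of change are not shown to reverse, and the Kruskal-Wallis test named for them cannot be recomputed from summary figures.

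**What to change.** - Regenerate outcome Tables 1–3 from the patient-level data, with n per row.
- Check each change SD against its pre/post bound and replace the left premolar inclination change SDs.
- Rerun the affected within-group and between-group tests, including the nasal floor molar baseline comparison.
- State the test actually used for each p-value: paired t or signed-rank within groups, and Kruskal-Wallis or ANOVA for change, since the table titles name ANOVA while the Statistical analysis section names Kruskal-Wallis.
- Correct the matching sentences in the Outcomes and pre-post sections, and revise any claim that does not survive.

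The cost is small: a re-export of three tables and a few SPSS reruns on existing data. Some p-values may become less favourable.
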